¹¹¹In-XYIMSR-01. In 2015 Wichert and co-workers identified a promising dual-motif inhibitor of CAIX from a DNA-encoded chemical [25]. We subsequently improved upon this agent by replacing the IRDye750 portion of their molecule with the hydrophilic species 1,4,7,10-tetraazacyclododecane-1,4,7,10-tetraacetic acid (DOTA), which enables convenient radiolabeling with metal isotopes for positron emission tomography (PET), single photon emission computed tomography (SPECT), and radiopharmaceutical therapy [26, 27]. We have termed this agent XYIMSR-01 have previously reported our pre-clinical experience with an indium-111 labeled (¹¹¹In) version of the molecule [27]. SPECT imaging of immunocompromised mice bearing CAIX-expressing SK-RC-52 tumors revealed radiotracer uptake in tumor as early as 1 hour post-injection. Biodistribution studies demonstrated 26% injected dose per gram of radioactivity within tumor at 1 hour. At 24 hours post-injection, Tumor-to- blood, muscle, and kidney, ratios were 178.1 ± 145.4 , 68.4 ± 29.0 and 1.7 ± 1.2 , respectively. Retention of radioactivity was exclusively

observed in tumors by 48 hours, the latest time point evaluated. In total, imaging with ^{111}In -XYIMSR-01 enabled specific detection of ccRCC in this xenograft model, with pharmacokinetics surpassing those of previously described radionuclide-based probes against CAIX.

Dosimetry. Using the biodistribution data generated in the paper by Yang et al. we have estimated the human dosimetry for ^{111}In -XYIMSR-01 agent.

Target Organs	Organ Dose (rem/mCi)	Organ Dose (mSv/MBq)
Adrenals	1.60E-01	4.31E-02
Brain	3.82E-02	1.03E-02
Breasts	6.07E-02	1.64E-02
Gallbladder Wall	1.54E-01	4.15E-02
Lower Large Intestine	1.24E-01	3.36E-02
Small Intestine	1.38E-01	3.73E-02
Stomach Wall	1.47E-01	3.97E-02
Upper Large Intestine	1.21E-01	3.28E-02
Heart Wall	1.38E-01	3.74E-02
Kidneys	4.74E-01	1.28E-01
Liver	1.79E-01	4.84E-02
Lungs	3.43E-01	9.28E-02
Muscle	1.67E-01	4.51E-02
Ovaries	1.39E-01	3.74E-02
Pancreas	1.72E-01	4.65E-02
Red Marrow	1.00E-01	2.71E-02
Osteogenic Cells	1.47E-01	3.98E-02
Skin	6.19E-02	1.67E-02
Spleen	1.59E-01	4.30E-02
Testes	9.07E-02	2.45E-02
Thymus	1.23E-01	3.32E-02
Thyroid	1.14E-01	3.08E-02
Urinary Bladder Wall	1.29E-01	3.49E-02
Uterus	1.35E-01	3.66E-02
Total Body	1.34E-01	3.63E-02

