3.2 Eligibility Criteria

Inclusion Criteria:

1. Males or female sex
2. ≥ 18 years of age
3. Willingness to provide signed informed consent and comply with all protocol requirements
4. Histological confirmation of RCC with a clear cell component
5. 2-10 sites of disease measuring ≥ 1.5 cm on contrast-enhanced CT and/or MRI imaging of the chest, abdomen and pelvis performed ≤ 60 days prior to the date of study enrollment
6. Screening clinical laboratory values as specified below:
 - Serum bilirubin ≤ 1.5 times the upper limit of normal. For patients with known Gilbert's syndrome, $\leq 3 \times \text{ULN}$ is permitted
 - ALT ≤ 3 times the upper limits of normal
 - AST ≤ 3 times the upper limits of normal
 - Creatinine clearance ≥ 50 mL/min based on Cockcroft-Gault formula
 - Absolute neutrophil count $\geq 1,500 / \text{mm}^3$
 - Platelets $\geq 100,000 / \text{mm}^3$
 - Hemoglobin $\geq 9.0 \text{ g/dL}$
 - White blood cell count $\geq 2,000 / \text{mm}^3$

Exclusion criteria:

- Systemic therapy for the treatment of ccRCC within 12 months of study enrollment.
- Subjects administered any radioisotope within five physical half-lives prior to study drug injection.
- Subjects with any medical condition or other circumstances that, in the opinion of the investigator, compromise obtaining reliable data, achieving study objectives, or completion.
- Women of child-bearing potential (WOCBP) must have a negative serum or urine pregnancy test (minimum sensitivity 25 IU/L or equivalent units of human chorionic gonadotropin) within 24 hours prior to the imaging day.
- Women must not be breastfeeding.

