7.2 Secondary Objectives

Biodistribution and Radiation Dosimetry: A secondary objective of this study is to determine the biodistribution and radiation dosimetry of ^{111}In -XYIMSR-01. To allow for this, SPECT/CT images will be acquired at 2-4, 24 ± 1 hour, and 48 ± 1 hour post-injection. For the first three patients a total of three fields of view will be acquired and for the remaining 7 patients two fields of view will be acquired. Each SPECT acquisition will be acquired over a 20-30 minute period. The first time point acquisition for each field of view will include a high resolution CT. All other time points will be acquired with a low-dose CT.

The acquired PECT/CT images will be used to perform the biodistribution and radiation dosimetry calculations. Time-activity curves (TACs) demonstrating radiotracer activity as a function of time post injection (minutes) will be drawn for the whole body and the following organs: brain, breast, gallbladder, stomach, pancreas, heart wall, lung, liver, bladder, muscle, pancreas, red marrow, spleen, adrenals, upper large intestine, lower large intestine, small intestine, thymus, thyroid, testes and ovaries. Individual organ residence times will be calculated by fitting an exponential function to the TAC data and analytically integrating the fitted functions from zero to infinity. Organ specific mean radiation-absorbed dose estimates for ^{111}In -XYIMSR-01 will be calculated from the individual organ residence times. Reference organ mass values will be adjusted based on actual organ masses. The OLINDA software package will be used to determine the absorbed dose [28].

Characterization of Pharmacokinetics: The pharmacokinetic profile of ^{111}In -XYIMSR-01 will be determined as a secondary endpoint of the study. ~5 mL of blood will be collected in heparinized tubes at pre-dose, 5 ± 2 minutes, 10 ± 2 minutes, 20 ± 5 minutes, 30 ± 5 minutes, 1 ± 0.25 hour, 1.5 ± 0.25 hour, and 24 hours ± 1 hour, post-injection to estimate elimination half-life. The collected blood will be evaluated for total radioractivity, the ratio of free versus protein-bound radiotracer, and measurement of the relative percentage of radiotracer and its metabolites.

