Comparison with Anatomical Imaging: As an initial assessment of the diagnostic performance of ^{111}In -XYIMSR-01 SPECT/CT, findings on this novel imaging test will be compared to those on conventional imaging (CT and/or MRI). Using descriptive statistics we plan to summarize the number of lesions that are detected with all imaging modalities, the number of lesions detected

with ^{111}In -XYIMSR-01 SPECT/CT but not with conventional imaging, and the number of lesions detected with conventional imaging but not by ^{111}In -XYIMSR-01 SPECT/CT.

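### The biodistribution plan covers normal organs and the lesion analysis only counts detections, so tumour uptake, retention and contrast are not planned measurements

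*Combined protocol and SAP*

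**What the plan says.** Under Biodistribution and Radiation Dosimetry, Section 7.2 states that "SPECT/CT images will be acquired at 2-4, 24 ± 1 hour, and 48 ± 1 hour post-injection", and that the "images will be used to perform the biodistribution and radiation dosimetry calculations". Time-activity curves "will be drawn for the whole body and the following organs: brain, breast, gallbladder, stomach, pancreas, heart wall, lung, liver, bladder, muscle", and the list then runs "pancreas, red marrow, spleen, adrenals, upper large intestine, lower large intestine, small intestine, thymus, thyroid, testes and ovaries". What is derived from the curves also concerns organs: "Individual organ residence times will be calculated by fitting an exponential function to the TAC data", and these residence times lead to organ absorbed doses.

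Lesions appear only under Comparison with Anatomical Imaging in the same section: "Using descriptive statistics we plan to summarize the number of lesions that are detected with all imaging modalities", plus the number seen by SPECT/CT alone and the number seen by conventional imaging alone.

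Section 1.1 presents the preclinical case for the agent: "Biodistribution studies demonstrated 26% injected dose per gram of radioactivity within tumor at 1 hour". It adds tumour-to-blood, tumour-to-muscle and tumour-to-kidney ratios at 24 h, and retention in tumour alone by 48 h. Section 2.2 names biodistribution and dosimetry, pharmacokinetics, and concordance with conventional imaging as the secondary objectives. Section 3.2 requires "2-10 sites of disease measuring" at least 1.5 cm.

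**The concern.** The agent is meant to bind tumour. Section 1.1 says that most earlier small-molecule agents for this target reached tumour poorly and accumulated elsewhere, and then argues that this agent does better on both counts. The human plan measures the second of these (normal organs) and has no measurement of the first.

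A count of detected lesions does not fill the gap. It records whether a lesion was seen, not by how much it stood out or whether activity stayed in it from 2 to 48 h. If most lesions are seen, the count cannot rank faint against intense ones. If many are missed, it cannot say whether the lesion took up little tracer or the surrounding tissue took up a lot. In either case, the trial would end without a planned answer on whether the preclinical contrast carries over to patients.

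**Working it through.** The plan gives no figure on this point to reproduce. The check is a reading of the analysis text, followed by simple counts.

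**1. Region list (Section 7.2).** From brain to muscle there are 10 organ entries, and from the second mention of pancreas to ovaries there are 11. So 10 + 11 = 21 entries. Pancreas appears twice, which leaves 20 distinct organs plus the whole body. Tumour, lesion or metastasis entries: 0. Kidney entries: 0, although Section 1.1 calls the kidneys dose limiting.

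**2. Other imaging analyses.** The only other one is the set of three lesion counts. No section plans a lesion uptake value, a lesion time-activity curve or a tumour-to-background ratio.

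**3. Preclinical quantity against planned human counterpart.**

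| Section 1.1 (mouse) | Planned in patients |
|---|---|
| Tumour uptake, 26% injected dose per gram at 1 h | none |
| Tumour-to-blood 178.1 ± 145.4 at 24 h | blood sample at 24 h, no tumour value |
| Tumour-to-muscle 68.4 ± 29.0 at 24 h | muscle curve, no tumour value |
| Tumour-to-kidney 1.7 ± 1.2 at 24 h | neither region |
| Retention in tumour alone by 48 h | scan at 48 h, no tumour value |

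**4. What the planned scans could yield.**
- Imaging time points: 10 patients × 3 = 30.
- Field-of-view acquisitions, with three fields in the first 3 patients and two in the other 7: 3 × (3 × 3 + 7 × 2) = 3 × 23 = 69.
- Eligible lesions: 10 × 2 = 20 to 10 × 10 = 100.
- Lesion-by-time values: 20 × 3 = 60 to 100 × 3 = 300, assuming that every eligible lesion is in field and every patient completes all three scans.

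**5. Which ratios have a matching reference.**
- Muscle is already a listed region. The kidneys would have to be added.
- Blood is drawn up to 1.5 h and then at 24 h. The latest early draw is at 1.5 + 0.25 = 1.75 h by Section 7.2, or 90 + 25 = 115 minutes by the time-point table in Section 4. Both precede the scan that opens at 2 h, and no blood is drawn at 48 h.
- At 24 h, both the sample and the scan fall between 23 and 25 h. Tumour-to-blood therefore has a matching sample at 24 h only, which is also the time of the mouse ratio.

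**The case against.** The strongest reply is that nothing in the plan is wrong. Tumour uptake is not a named objective, every secondary objective in Section 2.2 has an analysis, and the region list serves a normal-organ dose calculation. That stands in part: this is an omission relative to the rationale and to the biodistribution objective, not a contradiction. It does not remove the point, because Section 1.1 itself reports uptake in tumour as a biodistribution finding.

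A reader might infer several stronger things that the documents do not support:

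- **That the trial can never measure tumour uptake.** Lesion counts are a yes/no reading of visible uptake, and Section 9.2 archives the images, so later quantification remains possible. What is lost is a measurement fixed in advance, which guards against choosing the best-looking lesions afterwards.
- **That tumour was deliberately excluded.** The list repeats pancreas and omits the kidneys, so a missing entry may be a drafting slip.
- **That the count will sit at its ceiling.** The figure of about 95% in Section 1.1 is target overexpression in tumour specimens, not visibility on SPECT. The same section reports low uptake for most earlier agents, and the lesion counts are not restricted to 1.5 cm or more. A high or a low count is possible.
- **That 60 to 300 values are already in hand.** Seven of 10 patients have two fields of view, their placement is not stated, and eligible disease may lie anywhere in chest, abdomen or pelvis.

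Two technical objections also stand. The documents describe no SPECT calibration; that the scans can be quantified is inferred from their use for activity curves and dosimetry. And percent injected activity per mL in a patient is not directly comparable with the mouse figure per gram without scaling for body mass. The mouse figure is also from 1 h, before the first human scan.

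**Conclusion.** The point holds as an omitted measurement. Section 7.2 plans curves for the whole body and 20 distinct normal organs and counts of detected lesions, and nothing that quantifies tumour uptake, retention or contrast. It is a cheap improvement rather than an error: safety, organ dosimetry, pharmacokinetics and concordance can all be reported without it.

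Its size is bounded by eligibility and imaging: 20 to 100 eligible lesions, and 60 to 300 lesion-by-time values if all of them are in field. The true yield may be lower at either end and cannot be worked out from the documents. The conclusion rests on reading the region list as complete and on the scans being quantifiable, which the planned dosimetry requires in any case.

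**What to change.** In Section 7.2:

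- Add as regions all qualifying lesions of at least 1.5 cm that lie within the acquired fields of view, outlined on the first-time-point CT. Add the kidneys.
- Report percent injected activity per mL, and the tumour-to-muscle and tumour-to-kidney ratios, at 2-4, 24 and 48 h where the reference region is in field.
- Report tumour-to-blood at 24 h only, using the 24 ± 1 h blood sample. State how image and blood activity are put on the same scale.
- Give the number of lesions in field out of those eligible, and show lesion size beside each value.
- Summarise as the within-patient median, then across the 10 patients with a range, so that patients with many lesions do not dominate.

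This needs no extra scan, visit, blood draw or radiation exposure. The cost is wording and contouring time. Values will read low in lesions near 1.5 cm because of limited SPECT resolution; showing lesion size makes this visible but does not correct it.

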Based on the presented data, we have determined the kidneys to be dose limiting at 0.474 rem/mCi. In accordance with the guidance found in 21 CFR 361.1, 10.55 mCi may be administered to patients in this study.

Toxicology. The toxicology of cold $^{113}/^{115}\text{In}$ -XYIMSR-01 has been studied. Administration of $^{113}/^{115}\text{In}$ -XYIMSR-01 at doses of 11 and 55 $\mu\text{g}/\text{kg}$ was well tolerated by male and female Sprague-Dawley rats. No consistent or treatment-related effects were observed with respect to the following endpoints: survival; clinical signs; body weight; clinical chemistry, hematology,

IRB number: IRB00237314

Version: 3.0 Date: February 22, 2025

and urinalysis parameters; absolute or relative organ weights; or histopathology. These data support the safety of administering ^{111}In -XYIMSR-01 to human subjection.

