2. OBJECTIVES

2.1 Primary Objectives:

The primary objective of this study is to evaluate the safety, tolerability, and feasibility of ^{111}In -XYIMSR-01 SPECT/CT in patients with metastatic ccRCC.

2.2 Secondary Objectives:

- To determine the biodistribution and radiation dosimetry of ^{111}In -XYIMSR-01.
- To characterize the pharmacokinetics of ^{111}In -XYIMSR-01.
- To assess the concordance of findings on ^{111}In -XYIMSR-01 SPECT/CT with conventional imaging.

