⁷ SPECT/CT will be acquired at 2-4, 24± 1 hour, and 48± 1 hour post-injection. For the first three enrolled patients, a total of three fields of view will be acquired and for the remaining 7 patients two fields of view will be acquired. Each SPECT acquisition will be acquired over a 20-30 minute period.

⁸ A safety phone call will also occur 7(±3) days post-dosing. Ongoing adverse events thought to be related to ¹¹¹In-XYIMSR-01 will be followed until resolution of the adverse event, until an alternate cause has been identified, the patient is lost to follow-up, the patient withdraws consent, or it has been determined that ¹¹¹In-XYIMSR-01 is not the cause of the adverse event.

⁹ In order to minimize the need for research-only in-person visits, telemedicine visits may be substituted for in-person research study visits or portions of research study visits where determined to be appropriate and where determined by the investigator not to increase the participants' risks. Prior to initiating telemedicine for study visits the study team will explain to the participant, what a telemedicine visit entails and confirm that the study participant is in agreement and able to proceed with this method. Telemedicine acknowledgement will be obtained in accordance with the Guidance for Use of Telemedicine in Research. In the event telemedicine is not deemed feasible, the study visit will proceed as an in-person visit. Telemedicine visits will be conducted using HIPAA compliant method approved by the Health System and within licensing restrictions.

¹⁰ Safety blood tests: comprehensive metabolic panel to monitor blood chemistries, including kidney and liver function, and blood cell count will be collected at the end of 48 hour SPECT/CT imaging.

¹¹ A 12-lead electrocardiogram will be conducted at the end of 48 hour SPECT/CT imaging.

Pharmacokinetics & Imaging Timepoints:

Procedure	Pre-dose	0 hour	5± 2min.	10± 2 min.	20± 2 min.	30± 5 min.	60± 25 min.	90± 25 min.	2-4 hour	24± 1 hour	48± 1 hour
¹¹¹ In-XYIMSR-01 Administration		X									
Blood & Plasma Collection	X		X	X	X	X	X	X		X	
¹¹¹ In-XYIMSR-01 SPECT/CT Imaging									X	X	X

5. CRITERIA FOR DISCONTINUATION: CANCELLATION/WITHDRAWL PROCEDURES AND EARLY STOPPING RULES.

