9.2 Data Management

Imaging data will be stored on our university radiology archives system. Source documentation will be maintained by site study staff to support the patient research record.

The confidentiality of records that could identify subjects must be protected, respecting the privacy and confidentiality rules in accordance with the applicable regulatory requirement(s).

Every effort will be made to maintain the anonymity and confidentiality of all patients during this clinical study. However, because of the experimental nature of this investigational product, the Investigator agrees to allow the IRB, and authorized employees of appropriate regulatory agencies to inspect the facilities used in this study and, for purposes of verification, allow direct access to the study site records of all participants enrolled into this study.

The Investigator will assure that each participant's anonymity will be strictly maintained and that each participant's identity is protected from unauthorized parties.

Participants will be assigned a numerical code by the study team. The code list is kept secure and confidential by the study team on physically secured servers. Sufficient information will be retained at the study site to permit sample data and data to be connected with the unique participant number assigned to each study participant.

Data security will be controlled through appropriate restriction of access to only individual users to accomplish their roles in the data management process.

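### The organ list for time-activity curves in section 7.2 leaves out the kidneys, which the protocol calls dose limiting, so the dosimetry as written yields no measured human kidney dose.

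*Combined protocol and SAP*

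**What the plan says.** Section 2.2 makes dosimetry a secondary objective: "To determine the biodistribution and radiation dosimetry of" the tracer.

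Section 7.2 sets out how this will be done. Curves of activity against time are drawn for the whole body and for a list of named organs. The list begins "brain, breast, gallbladder, stomach, pancreas, heart wall, lung, liver, bladder, muscle, pancreas, red marrow, spleen, adrenals" and ends with the upper and lower large intestine, small intestine, thymus, thyroid, testes and ovaries. An exponential function is fitted to each curve and integrated to give a residence time, and organ doses "will be calculated from the individual organ residence times" using the OLINDA software.

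Section 1.1 reports the dosimetry available before the study. From preclinical biodistribution data, "we have estimated the human dosimetry for" the tracer, with coefficients tabulated for 24 organs and the total body. The text below the table concludes: "we have determined the kidneys to be dose limiting at 0.474 rem/mCi". It then gives 10.55 mCi as the activity that may be administered.

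On acquisition, footnote 7 of the section 4 schedule gives three fields of view for the first three patients and says that "for the remaining 7 patients two fields of view will be acquired". The anatomical position of the fields is not stated.

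**The concern.** The organ that the protocol identifies as limiting is missing from the list of organs to be measured. The list is worded as complete, not as a set of examples, and each step depends on the one before it: no curve means no residence time, and no residence time means no dose based on that organ's own uptake.

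The existing kidney figure is a projection to humans from preclinical data. Checking such a projection in patients is a large part of what a first dosimetry study is for. As written, the study would measure the lungs, thymus and thyroid but leave the kidney projection untested.

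**Working it through.** **The plan's own kidney figure.** Inputs, all from section 1.1: kidney coefficient 0.474 rem/mCi (0.128 mSv/MBq) and permitted activity 10.55 mCi.

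- Unit check: 0.474 × 10/37 = 0.128 mSv/MBq, as tabulated.
- Link between coefficient and activity: 10.55 × 0.474 = 5.00 rem, and in reverse 5/0.474 = 10.549, which rounds to 10.55 mCi. The 5 rem value is not printed; the two printed figures imply it. The stated activity is therefore consistent with having been set from the kidney coefficient.

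**List against table.** The section 7.2 list has 14 entries in the part quoted above and 7 after it, so 21. Pancreas occurs twice, which leaves 20 distinct organs. The section 1.1 table has 24 organs besides total body. All 20 listed organs are in the table, so 24 − 20 = 4 have no planned curve:

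| Organ without a planned curve | Projected rem/mCi |
|---|---|
| Kidneys | 0.474 |
| Osteogenic cells | 0.147 |
| Uterus | 0.135 |
| Skin | 0.0619 |

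The kidney coefficient is the highest of all 24. The highest organ that is on the list is the lung at 0.343, and 0.474/0.343 = 1.38.

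**Is the kidney covered elsewhere?** No other section plans a kidney curve, residence time or dose. The blood chemistry in section 4 monitors kidney function, which is not dosimetry. The whole-body curve includes kidney activity but does not isolate it.

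**Size of the projection that would go unchecked.** Sections 4 and 6.1.1 plan 10.5 ± 1 mCi:

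- 9.5 × 0.474 = 4.50 rem
- 10.5 × 0.474 = 4.98 rem
- 11.5 × 0.474 = 5.45 rem

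These are projected doses, not an error caused by the omission. (As a separate point, 11.5 mCi lies above the 10.55 mCi in section 1.1, and those sections must be reconciled.)

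**Supporting evidence.** The 24-hour mouse ratios of tumour to blood, muscle and kidney in section 1.1 end "muscle, and kidney, ratios were 178.1 ± 145.4 , 68.4 ± 29.0 and 1.7 ± 1.2". Dividing the muscle ratio by the kidney ratio gives 68.4/1.7 = 40, an implied kidney-to-muscle ratio. It is rough: it divides two mean ratios, and the kidney SD is 1.2/1.7 = 71% of its mean. The conclusion does not depend on it.

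**The case against.** The strongest reply is that this is a drafting slip. The dosimetry objective is unrestricted, section 7.2 does not forbid further organs, section 1.1 itself singles out the kidneys, and the repeated pancreas suggests that one entry was mistyped. The images are also kept: "Imaging data will be stored on our university radiology archives system". A kidney curve could therefore be drawn later. A slip is plausible, but the documents do not confirm it, and an analyst who follows section 7.2 would still omit the kidneys. Later analysis is possible only where the kidneys were in view, which the documents do not establish for any patient. No acquisition failure is shown either; the demonstrated gap is in the analysis text.

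A second reply is that the software may print a kidney value anyway. That is fair, and the point is not that no number would appear. Any such number would not rest on measured kidney uptake.

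Third, the mouse evidence is weak, and section 1.1 adds that by 48 hours activity was retained only in tumour. This stands as a caution against leaning on the mouse ratios; the dose-limiting statement is enough by itself.

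Fourth, a kidney contour is not always simple. Section 3.2 neither requires nor excludes a previous nephrectomy or a primary tumour in place, and tumour inside the contour would add its own uptake of a CAIX-targeted tracer. This stands, and the fix should deal with it.

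**Conclusion.** The concern holds. As written, section 7.2 plans no curve, and so no measured dose, for the one organ of 24 that has the highest projected coefficient and that the protocol calls dose limiting. A secondary objective is incomplete at its most important organ. It should be fixed; the primary safety analysis and the sample size of 10 are unaffected.

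The conclusion rests on reading the list as complete, which is how it is worded, and on the plan's own sequence from curve to residence time to dose. The effect of the omission on the dose estimates for other organs cannot be calculated from the documents.

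**What to change.** In section 7.2:

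1. Add the kidneys to the time-activity-curve list and delete the second pancreas.
2. State that the kidneys are entered as a source organ in OLINDA.
3. Report the human kidney dose per mCi beside the 0.474 rem/mCi projection.
4. State whether the fields of view include the kidneys, especially for the seven patients with two fields. If not all do, report the kidney dose from the patients in whom they are in view, with that number.
5. State how a patient with one kidney, or with tumour within a kidney, is contoured and whether that patient enters the kidney summary.

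The cost is a text edit and kidney contours on at most 10 patients × 3 time points = 30 image sets, with more effort where tumour must be separated from normal kidney. Kidney coverage should be confirmed first, while any remaining patients can still be imaged accordingly. For patients already scanned with the kidneys in view, the archived images would allow the curve to be drawn.

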4. STUDY PROCEDURES

	Screening/ Baseline ⁹	¹¹¹ In- XYIMSR-01 Dosing and SPECT/CT Imaging	¹¹¹ In-XYIMSR-01 SPECT/CT	Follow-Up visit
	Day-30 to Day 1	Day 1	Day 2, and Day 3 post-injection (24± 1 hour, and 48± 1 hour post-injection)	Within 7 Days from ¹¹¹ In-XYIMSR-01 Administration
Informed Consent & Eligibility	X			
Demographics (date of birth, race, ethnicity)	X			
Medical History	X			
Vital Signs (Blood Pressure, Heart Rate, Temperature) ¹	X	X ¹	X	
Height and weight	X	X	X	
Clinical Labs (Hematology, Chemistry) ²	X	X	X ¹⁰	
Urinalysis	X			
Pregnancy test ³	X	X		
Study Sample Collection ⁴		X		
12-Lead Electrocardiogram (ECG)	X	X ⁵	X ¹¹	
¹¹¹ In-XYIMSR-01 Administration ⁶		X		
SPECT/CT ⁷		X	X	
Adverse Events		X	X	X
Concomitant Medications	X	X	X	X
Standard-of-care Conventional Imaging Review	X			X
Standard-of-care Archived Tumor Tissue or Recent Tumor Biopsy	X			
Follow-Up phone call ⁸				X

¹ On Day 1 Vital Signs (Blood Pressure, Heart Rate, Temperature) will be performed before ¹¹¹In-XYIMSR-01 Administration injection and at the end of ¹¹¹In-XYIMSR-01 SPECT/CT

² Standard of care comprehensive metabolic panel to include measurement of sodium, potassium, chloride, bicarbonate, BUN, creatinine, glucose, total bilirubin, calcium, total protein, albumin, AST, ALT, and alkaline phosphatase.

Standard of care CBC: WBC differential (neutrophils, lymphocytes, monocytes, eosinophils, basophils), WBC count, RBC count, Hematocrit, Hemoglobin, Platelets.

³ For females of childbearing potential, a negative serum or urine pregnancy test will be obtained within a 24-hour period prior to SPECT/CT study.

⁴ Blood samples will be collected at the following time points: pre-dose, 5±2 minutes, 10±2 minutes, 20±5 minutes, 30±5 minutes, 1±0.25 hour, 1.5±0.25 hour, and 24 hours ± 1 hour, post-injection to estimate elimination half-life. About 5 mL of blood will be collected in a heparinized tube at each time point via a peripheral vein.

⁵ A 12-lead electrocardiogram will be performed just prior to ¹¹¹In-XYIMSR-01 administration and immediately following SPECT/CT imaging

⁶ Patients will receive 10.5±1 mCi of radiotracer via an intravenous catheter placed in an antecubital vein or an equivalent venous access.

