6.1.1 Drug Substance

Common Name: ^{111}In -XYIMSR-01

Unit Dose: 10.5 ± 1 mCi of ^{111}In -XYIMSR-01 followed by SPECT/CT imaging

Route of administration: Intravenous catheter placed in an antecubital vein or an equivalent venous access

6.1.2 ^{111}In -XYIMSR-01 Manufacturer

The radiotracer will be manufactured at the Center for Translational Molecular Imaging located

at [name].

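### The human dosimetry list leaves out the kidneys, the organ that sets the activity, and the 10.5±1 mCi window runs above the protocol's own 10.55 mCi

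*Combined protocol and SAP*

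**What the plan says.** Section 1.1 tabulates human organ doses estimated from preclinical biodistribution. It then concludes: "Based on the presented data, we have determined the kidneys to be dose limiting at 0.474 rem/mCi". The next sentence sets the activity: "In accordance with the guidance found in 21 CFR 361.1, 10.55 mCi may be administered to patients in this study".

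Radiation dosimetry is a secondary objective (Section 2.2). Section 7.2 says that time-activity curves will be drawn for the whole body and for a stated list of organs: "brain, breast, gallbladder, stomach, pancreas, heart wall, lung, liver, bladder, muscle, pancreas, red marrow, spleen, adrenals, upper large intestine, lower large intestine, small intestine", followed by "thymus, thyroid, testes and ovaries". An exponential is fitted to each curve to give a residence time, and the organ doses "will be calculated from the individual organ residence times".

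On imaging, Section 7.2 says: "For the first three patients a total of three fields of view will be acquired and for the remaining 7 patients two fields". It does not say where the fields are placed.

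On activity, footnote 6 to the calendar in Section 4 says: "Patients will receive 10.5±1 mCi of radiotracer via an intravenous catheter". Section 6.1.1 repeats it ("Unit Dose: 10.5 ± 1 mCi of"), and Section 8.1 uses the same window when it states the radiation risk. No section adds a separate upper cap.

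**The concern.** The kidney coefficient is the number that justifies the administered activity, and it has not been measured in humans. Checking it is an obvious use of the dosimetry objective. The preclinical results in Section 1.1 point the same way: the 24-hour tumour-to-kidney ratio was 1.7, against 68.4 for muscle and 178.1 for blood, so of these three tissues the kidney came closest to tumour. Yet the kidneys are missing from the list of organs to be measured. If the list is followed, the human dosimetry report will not address the organ on which the activity rests.

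The second problem is separate. An activity derived from a dose-limiting organ and tied to a cited regulation reads naturally as a ceiling. The tolerance around 10.5 mCi crosses it. A patient given, say, 11 mCi would be within the dosing instruction and above the figure that Section 1.1 derives, whatever the true human uptake turns out to be.

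**Working it through.** **Inputs.** Kidney coefficient 0.474 rem/mCi and derived activity 10.55 mCi (Section 1.1); window 10.5±1 mCi, that is 9.5 to 11.5 mCi (Sections 4, 6.1.1 and 8.1); organ list (Section 7.2). The rem limit is not printed, so it is back-solved here.

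**Step 1: reproduce the plan's activity.** Implied limit = 10.55 × 0.474 = 5.0007 rem. In the other direction, 5 / 0.474 = 10.549, which rounds to 10.55 mCi. The stated figure is reproduced if the organ limit is 5 rem.

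**Step 2: kidney dose across the window.** Dose = activity × 0.474.

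| Activity (mCi) | Kidney dose (rem) | Relative to 10.55 mCi |
|---|---|---|
| 9.5 | 4.50 | 10.0% below |
| 10.5 | 4.98 | 0.5% below |
| 10.55 | 5.00 | equal |
| 11.5 | 5.45 | 9.0% above |

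The excess at the top is 11.5 − 10.55 = 0.95 mCi, and 11.5 / 10.55 − 1 = 9.0%. The comparison in mCi does not depend on the back-solved 5 rem.

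**Step 3: what window would fit.** A ±1 mCi tolerance stays at or below 10.55 mCi only if the target is at most 10.55 − 1 = 9.55 mCi. With a 10.5 mCi target, the upward tolerance is only 10.55 − 10.5 = 0.05 mCi. Two windows that fit:

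- 9.5±1 mCi: 8.5 to 10.5 mCi, kidney 4.03 to 4.98 rem, target change 9.5 / 10.5 − 1 = −9.5%.
- 10.0±0.5 mCi: 9.5 to 10.5 mCi, kidney 4.50 to 4.98 rem, target change 10.0 / 10.5 − 1 = −4.8%.

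**Step 4: read the organ list.** The two quoted parts hold 17 and 4 entries, 21 in all. The pancreas is entered twice, so 20 organs are different. Kidneys are not among them, although 0.474 rem/mCi is the highest organ coefficient in the Section 1.1 table (the next is the lungs, 0.343).

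**Step 5: follow the chain in Section 7.2.** Curve, then fitted residence time, then dose. With no kidney curve there is no kidney residence time, and any kidney figure that the software returned would not rest on measured kidney activity. A whole-body curve does not replace it. No other section adds the kidneys to the analysis.

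**The case against.** The omission looks like a drafting slip: the repeated pancreas may stand where kidneys was meant. The SPECT/CT scans are planned anyway, and Section 9.2 keeps the images in the radiology archive, so a kidney curve could be drawn later if the kidneys were in view. The list also requires adrenals, spleen, liver and pancreas, so the upper abdomen has to be imaged. All this is fair, and it makes the omission easy to repair. It does not change what the written list would produce. A reader might infer that the kidneys will not be imaged. The documents do not support that: placement is unstated for every organ.

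On activity, Section 1.1 says what may be given and does not use the word maximum. The regulation is not reproduced, so whether it allows a dispensing tolerance cannot be judged here. The excess is at most 9.0%, on a coefficient that is itself extrapolated. This limits the size of the point, but the mismatch between the two figures remains, and nothing in the protocol explains it. A reader might note that 0.95 of the 2.0 mCi window (47.5%) lies above 10.55 mCi and infer that about half the patients would exceed it. That is a share of width, not of patients; no dispensing spread is given.

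Safeguards exist: creatinine clearance of at least 50 mL/min at entry (Section 3.2), chemistry after the 48-hour scan (Section 4, footnote 10) and monthly meetings (Section 9.1). They are useful, but none measures absorbed dose. The only written halt or pause trigger is related grade 3-5 toxicity (Sections 5.4, 7.3 and 8.1).

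**Conclusion.** Both inconsistencies stand, and both are errors in the plan as written rather than missing detail. Section 7.2 gives no human kidney dose from measured activity, although Section 1.1 rests the activity on that organ. The dosing window permits up to 11.5 mCi, 9.0% above the derived 10.55 mCi, or 5.45 rem against an implied 5.00 rem to the kidneys on the protocol's own coefficient. The nominal 10.5 mCi complies.

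The conclusion rests on reading 10.55 mCi as a ceiling and on taking the organ list as closed. The rem figures also assume the back-solved 5 rem limit and the preclinical coefficient.

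Three stronger readings might be inferred and are not supported. The documents do not show kidney harm at these activities, or that the human coefficient is higher than estimated. They plan no dose escalation, so an incomplete organ report would not by itself lead to higher activities in this trial. And they tie no decision to interim dosimetry, so waiting for early kidney doses before further accrual would be a preference, not a correction.

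**What to change.** **Organ list.** In Section 7.2, replace the second pancreas with kidneys. State that normal kidney will be contoured at 2-4, 24 and 48 hours on the planned scans, excluding any renal tumour. Section 3.2 does not exclude renal lesions, and uptake by a CAIX-expressing tumour could inflate the kidney estimate. Require the kidneys in view at least in the three patients with three fields, and in the two-field patients where placement allows. An absolute requirement in the two-field patients could cost chest or pelvic coverage, which the lesion comparison in Section 7.2 needs.

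**Activity.** State that administered activity will not exceed 10.55 mCi. Align footnote 6 of Section 4, Section 6.1.1 and Section 8.1, for example with 9.5±1 or 10.0±0.5 mCi, and check the radiation figure in Section 8.1 against the new target. It would help to print the organ limit behind 10.55 mCi in Section 1.1.

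**Cost.** The target falls by 9.5% or 4.8%, with slightly fewer counts. The narrower ±0.5 window may reject more prepared doses; the documents do not allow an estimate of how many. Contouring adds at most 10 patients × 3 time points = 30 readings. No extra scan, visit, patient or accrual pause is needed.
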